## **Primary objective and outcome**

The primary outcome is “days alive and out of hospital (DAOH) within 14 days after recruitment” defined as the time from hospital discharge and days without hospitalization up to 14 days from recruitment where the patient is alive. Data for the primary outcome analysis will be presented as mean [95%CI] and corresponding t-test and additionally for sensitivity analysis median [IQR] with corresponding non-parametric test, e.g. Mann-Whitney U-test

The estimation from the study group is that DAOH14 will be a number above or equal to 4. If DAOH14 is < 4, DAOH at 21 days will be presented instead. In this case, SD is estimated to not exceed 3.8 days, and the sample size should thus not be adjusted.

Apart from the main, unadjusted analysis, the primary outcome will be performed as an adjusted analysis using general linear models, while adjusting for the following variables: Age (per year increase), sex (M/F), COPD GOLD C/D (Yes vs. No), Heart failure NYHA III-IV (Yes vs. no), Active smoker (Yes vs. No).

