### 3.3.5. Statistical analyses:

#### Primary endpoint:

- Number of days alive and discharged from hospital within 14 days (summarises both whether the patient is alive and discharged from hospital) ("Days alive and out of hospital")

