### 3.3.6. Sample size:

#### Randomised controlled study

Prerequisite: Type 1 error rate = 5%. Power = 80%. Two-sided statistics. Group sequential design with one scheduled interim analysis after randomisation of 113 patients (50% recruitment).

Analysis: T-test.

Sample size is calculated based on the following estimates and indicative figures:

Expected duration of hospitalisation with COVID-19: 10 days

SD for "Days alive and discharged within 14 days" in patients with lung disease and COVID-19: 4 days (up to 10 days hospitalization)

Estimated time for improvement/deterioration: 1.5 days.

This requires 226 patients randomised 1:1 with 113 in each group. This is a fixed sample size. It is assumed that most patients complete the intervention.

However, for interim analysis, the Data and Safety Monitoring Board (DSMB) may recommend the steering committee to expand sample size.

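### The 14-day primary score ties death before discharge with a stay beyond day 14, and the planned rank-based sensitivity test keeps the tie

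*SAP*

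**What the plan says.** The protocol (section 3.3.5, Primary endpoint) counts days alive and discharged within 14 days and says that the count "summarises both whether the patient is alive and discharged from hospital". The SAP (Primary objective and outcome) gives the working definition: "defined as the time from hospital discharge and days without hospitalization up to 14 days from recruitment where the patient is alive". The main analysis is a comparison of means by t-test, "additionally for sensitivity analysis median [IQR] with corresponding non-parametric test, e.g. Mann-Whitney U-test".

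Neither section gives death a separate value or rank. The same kind of score is used in the adjusted linear model, in the 21-day version shown if DAOH14 falls below 4, and in the 30-day secondary outcome, which is analysed like the primary. The modified-ITT and per-protocol analyses change the population, not the score.

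Elsewhere the SAP does make provision for death. It is the lowest of the 8 hospital-status categories, days not alive are added to ICU days, and death is to be treated as a competing risk for readmissions and for days on non-invasive ventilation.

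**The concern.** A score described as summarising survival should respond when more patients in one arm die. For patients who would not have been discharged by day 14 anyway, this one cannot: they score 0 whether they live or die. A patient who dies after an early discharge keeps the days already earned and can rank above someone who survives.

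Both deaths and long stays are to be expected here. The protocol plans on a mean stay of 10 days (section 3.3.6) and cites an inpatient mortality estimate of 25% from early reports (section 2.1). Section 6 also states that death will not be treated as a serious adverse event, so the outcome analyses carry much of the task of showing a mortality difference. The sensitivity analysis is where one would look for protection against this weakness. As written, it addresses only the shape of the distribution, because it ranks the same numbers.

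**Working it through.** **1. The plan's own figure.** Inputs from protocol section 3.3.6: "Type 1 error rate = 5%. Power = 80%. Two-sided statistics"; SD of DAOH14 4 days; "Estimated time for improvement/deterioration: 1.5 days". The normal formula gives n per arm = 2 × (1.960 + 0.842)² × 4² / 1.5² = 111.6, so 112. The exact t-test gives 112.6, so 113 per arm and 226 in total, as stated. An assumed O'Brien-Fleming inflation of 1.008 for one interim look gives 227.0. The sample size is sound; the point concerns the scoring only.

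**2. The scoring rule applied.** Score = min(14, day of death) − day of discharge, less any readmitted days; 0 if never discharged.

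| Patient | Score | Alive at day 14? |
|---|---|---|
| Dies on the ward, day 5 | 0 | No |
| Dies on the ward, day 13 | 0 | No |
| Never discharged by day 14 | 0 | Yes |
| Discharged day 2, dies day 12 | 12 − 2 = 10 | No |
| Discharged day 6 | 14 − 6 = 8 | Yes |
| Discharged day 10 | 14 − 10 = 4 | Yes |
| Discharged day 2, readmitted day 4 to day 14 | 2 | Yes |

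The last row shows a limit: the tie at 0 concerns patients not discharged before day 14, not everyone in hospital on that day. Any rank test on these numbers leaves the zeros tied and ranks 10 (dead) above 8 and 4 (alive).

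**3. A fixed example (assumed).** Take 113 per arm, of whom 68 in each arm are discharged with the same scores from 1 to 12 (sum 426) and 45 score 0. Among those 45, control has 28 deaths and 17 inpatients; treatment has 6 deaths and 39 inpatients.
- As planned: both means are 426/113 = 3.77 (SD 4.06); t-test p = 1.00 and Mann-Whitney p = 1.00.
- Deaths alone, 28 v 6 of 113: Fisher's exact p = 0.00006.
- Death ranked below 0 days: treatment gains 39 × 28 = 1,092 pairs and loses 6 × 17 = 102. The win probability is 0.5 + (1,092 − 102)/(2 × 113²) = 0.539, p = 0.31.

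The mean of 3.77 is below 4, so strictly the SAP would present the 21-day version. That moves the tie to patients not discharged by day 21; it does not remove it.

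**4. How far this depends on who dies.** The documents give no distribution of stay, so one is assumed: gamma with mean 10 and shape 2, whole days counted, active stays 1.5 days shorter, 113 per arm, 3,000 simulated trials per scenario. Control DAOH14 then has mean 5.1, SD 4.2 and 27% at 0. Deaths are a share of the whole arm: 8% in both arms, then 8% control v 16% active. Figures are the chance of a significant benefit; ranges span repeated runs.

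| Who dies | Quantity | 8% v 8% | 8% v 16% |
|---|---|---|---|
| Only patients already at 0 | Mean difference | about 1.2 days | about 1.2 days |
| | t-test | 48–52% | 45–51% |
| | Mann-Whitney as planned | 48–51% | 47–50% |
| | Mann-Whitney, death worst | about 47% | about 36% |
| Patients at random (then scored 0) | Mean difference | 1.0–1.1 days | a little over 0.5 days |
| | t-test | about 40% | 11–14% |

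In the first block the planned tests cannot move, by construction; the small differences are simulation error. That block is an extreme. In the active arm the share at 0 is e^(−2.9) × 3.9 = 21.5%, so deaths in 16% of the arm mean that 16/21.5 = 74% of those patients die. Random placement is the opposite extreme.

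**5. What ranking death worst adds.** In a second assumed model (40% at 0 in both arms, scores 1 to 12 equally likely otherwise, 4,000 runs), treatment turns in-hospital deaths into inpatient survivors.

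| Deaths, control v treatment | Planned tests reject | Death-worst rank test rejects | Direct test of proportions, power |
|---|---|---|---|
| 25% v 12.5% | about 5% | 10% | 67% |
| 25% v 5% | about 5–6% | 19% | 99% |
| 15% v 5% | about 5% | 8% | 71% |
| 10% v 5% | about 5% | 6% | 30% |

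**The case against.** The strongest reply is that deaths are not hidden. The SAP gives frequencies for the 8 status categories, which collapse into dead, alive in hospital, and alive and out. It puts primary and secondary outcomes in one table, analyses 30-day mortality by log-rank test and Cox model, gives death its own Kaplan-Meier figure, and reports 30-day mortality at the interim. A rank comparison with death lowest is already secondary outcome 1, although the SAP names its test inconsistently. All of this stands, so no new display is needed.

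A second reply also stands. A reader might infer that the primary outcome takes no account of survival, so that a lethal drug could be declared beneficial without the plan showing it. The documents do not support this. A death in anyone who would otherwise have been discharged removes alive-and-out days, and random deaths roughly halve the assumed benefit. Only the primary test and its sensitivity test, read alone, miss deaths among would-be long stayers. How often a patient who dies after discharge would outscore survivors is unknown, since no rate is given.

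Third, putting a death-worst test in place of the Mann-Whitney test would lose the check on the t-test's distributional assumption, because it tests a different quantity. That is right, and it argues for adding the analysis, not substituting it.

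What the replies leave open is that no listed analysis of DAOH itself separates death from a long stay.

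**Conclusion.** The point holds in a limited form. That death before discharge ties with a stay beyond day 14, and that a death after early discharge can outscore a survivor, follows from the definition and needs no assumption. The protocol's statement that the score covers survival is therefore only partly true, and the planned rank test does not repair it.

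The practical size is uncertain. Under the assumed stay distribution, doubling deaths in the active arm changes the estimated benefit by anything from nothing to about half, depending on whether those who die would have gone home by day 14. The truth lies between, and the documents do not say where. The t-test, the sample size and the error rate are not in question. This is a cheap improvement to the sensitivity analysis, not a flaw that invalidates the primary outcome.

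**What to change.** Keep the t-test and the planned Mann-Whitney test on DAOH14. Before unblinding, add to the SAP one further rank-based sensitivity analysis in which any death within the window ranks below every survivor, including survivors with 0 days (for example, score −1). Do the same for the 30-day version, and for the 21-day version if that fallback is used. State that DAOH alone cannot tell death before discharge from a long stay, and that the primary result will be read beside the status-category frequencies and mortality already planned. The protocol assesses those categories on day 15 and the SAP at 14 days, so settle one day for that reading.

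The cost is one or two SAP sentences and one extra result per window, with no new data: dates of death are already needed for the Kaplan-Meier analysis. The downside is that the added test addresses a slightly different quantity and is only modestly sensitive to mortality (6–19% rejection in step 5). It supplements the direct mortality comparison and does not replace it. If it were first added after unblinding, it would look data-driven.

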### 3.3.2. Allocation:

The sponsor generates a randomisation sequence. Randomisation will be in blocks of unknown size and the final allocation will be via an encrypted website (REDCap), where also inclusion and exclusion criteria are required to be filled in correctly in order to randomise a patient.

Allocation will be stratified for age (>70 years vs. <=70 years), site of recruitment and whether the patient has any of the following chronic lung diseases: COPD, asthma, bronchiectasis, interstitial lung disease (Yes vs. No).

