6. Respiratory medicine department, Odense University Hospital, Odense, Denmark. pi: [name], Research Associate Professor, Senior Consultant in Respiratory Medicine
7. Respiratory medicine department, Aarhus- and Aalborg University, PI: [name], Research Associate Professor, Senior Consultant in Respiratory Medicine

Patients will be randomized to one of the two treatment arms:

- i) **Intervention group:** Azithromycin day 1-3: 500 mg x 1, day 4-15: 250 mg x 1  
Hydroxychloroquine: Day 1-15: 200 mg x 2
- ii) **Control group:** The control group will always receive the standard treatment and placebo for both types of intervention medication. If part or all the intervention therapy being investigated becomes standard treatment during the study, this may also be offered to the control group.

The analyses described in this document will be performed by [name], PhD coordinating investigator, in cooperation with the sponsor and principal investigator [name], research associate professor, Respiratory Medicine Section, University of Gentofte Hospital, once the data have been entered, cleaned and released for use.

This document provides a detailed description of the statistical analyses that will be performed for the evaluation of the primary and secondary endpoints of protocolized for the ProPAC-COVID study.

The analyses described in this document are compatible with the recommendations of the CONSORT 2010 statement.

The International Conference on Harmonisation (ICH) of Good Clinical Practice (GCP)(1) and leading experts recommend that randomized clinical trials should be analyzed according to predefined outcomes and a predefined detailed statistical analysis plan (2). To prevent selective reporting of outcomes and data-driven analysis results and increase transparency this paper will in detail describe the detailed statistical analysis plan for the ProPAC-COVID trial while enrolment of patients and collection of data is still on-going and before the database is accessed for trial results.

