### **Sample size**

The power to avoid type II error is 80% (1- $\beta$ ) at a two-sided 5% significance level, using a t-test for the primary outcome, and a group-sequential design allowing for one interim analysis at half target recruitment. This provides a sample size of 226 subjects. All confidence intervals reported will be 95% confidence intervals.

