## **Secondary objective and outcomes**

1. Categorization of hospitalization status [ Time Frame: 14 days]

The patient will be categorized into one of the following 8 categories depending on status of their hospitalization:

- a. Dead (yes/no)
- b. Hospitalized and receiving mechanical ventilation or Extra Corporal Membrane Oxygenation (ECMO) (yes/no)
- c. Hospitalized and receiving Non-invasive ventilation or "high-flow oxygen device" (yes/no)
- d. Hospitalized and given oxygen supplements different from (2) and (3) (yes/no)
- e. Hospitalized and without oxygen treatment, but receiving other treatment (both related to COVID-19 or other) (yes/no)
- f. Hospitalized for observation (yes/no)
- g. Discharged from hospital with restriction of activity level (yes/no)
- h. Discharged from hospital without any restrictions of activity level (yes/no)

For this analysis, the patient will be assigned a number between 1 and 8. Frequencies for the categories will be presented. Furthermore, the location on the scale for each group will be presented by median (IQR). Significance for differences will be calculated by a Wilcoxon-Sign-rank test (WSR).

Only one category can be "yes".

2. Admitted to intensive care unit, if admitted to ICU then length of stay [ Time Frame: 14 days]

Number of patients admitted to intensive care will be compared using chi-square test. Length of stay in ICU will be analyzed using a t-test. Days not alive within the time frame will be added to days at ICU. If days not alive are equal in the two treatment groups, we will further present days at ICU excluding days not alive.

3. Have used Non-invasive ventilation (NIV) during hospitalization [ Time Frame: 14 days]

Use of NIV will be compared by a chi-square test.

4. Mortality [Time Frame: 30 days ]

Differences in mortality will be displayed using the Kaplan-Meier plots method in combination with the log-rank test and as an adjusted analysis using Cox proportional hazards models, while adjusting for the following variables: Age (per year increase), sex (M/F), COPD GOLD C/D (Yes vs. No), Heart failure NYHA III-IV (Yes vs. no), Active smoker (Yes vs. No).

5. Length of hospitalization [ Time Frame: 14 days]

Length of hospitalization will be compared using t-test.

6. Days alive and discharged from hospital [ Time Frame: 30 days]

This is equal to the primary endpoint but with a longer time frame and will be analyzed like the that.

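### The primary t-test ignores the factors used to stratify randomisation, so if they are prognostic its confidence interval is wider than the design warrants

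*SAP*

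**What the plan says.** Protocol 3.3.2 stratifies allocation by age (above 70 or not) and by "site of recruitment and whether the patient has any of the following chronic lung diseases: COPD, asthma, bronchiectasis, interstitial lung disease". The lung-disease stratum is a single yes/no item covering all four conditions.

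The analysis does not follow this. Protocol 3.3.6 (Sample size) gives "Analysis: T-test", and the SAP (Sample size) repeats it: "using a t-test for the primary outcome, and a group-sequential design allowing for one interim analysis at half target recruitment". Under Primary objective and outcome, the SAP reports DAOH14 as means with a t-test and uses a rank test for sensitivity. It then continues: "Apart from the main, unadjusted analysis, the primary outcome will be performed as an adjusted analysis using general linear models". That model contains age in years, sex and "COPD GOLD C/D (Yes vs. No), Heart failure NYHA III-IV (Yes vs. no), Active smoker (Yes vs. No".

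Site is in no analysis of the primary outcome. Lung disease as stratified is used only to define a subgroup (SAP, Subgroup analyses). Neither document explains why the stratification factors are left out.

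The same approach carries over to two other outcomes. One is the fallback: "If DAOH14 is < 4, DAOH at 21 days will be presented instead". The other is the 30-day version (SAP, Secondary objective and outcomes, item 6): "This is equal to the primary endpoint but with a longer time frame and will be analyzed like the that". The interim analysis also reports the primary outcome, but the SAP names no test for it.

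**The concern.** Blocked allocation within strata keeps the arms balanced on age group, site and lung disease. Outcome variation due to those factors then largely cancels out of the difference in means. The t-test does not know this. It takes its standard error from the whole within-arm variance, including the part that the design has removed. If the factors are prognostic, the standard error is too large, the interval too wide and the true type I error below 5%. A real effect becomes somewhat easier to miss.

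The supplementary model does not close the gap. It is not the main analysis and it has no site term. Its lung-disease term also leaves out asthma, bronchiectasis, interstitial lung disease and COPD in GOLD A/B.

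**Working it through.** **Inputs from the documents.** Difference 1.5 days, SD 4, two-sided 5%, power 80%, 113 per arm, one interim look at half recruitment (Protocol 3.3.6); eight centres (SAP, Introduction); three stratification factors (Protocol 3.3.2). Eight sites × 2 × 2 gives 32 strata, about 7 patients each (226/32).

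**Input the documents do not give.** R², the share of DAOH14 variance explained by the stratification factors. It is varied below.

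**1. The plan's own figure.** n per arm = 2 × 4² × (1.960 + 0.842)² / 1.5² = 111.6, so 112. The exact t-test needs 113 per arm: power 80.1%, against 79.8% with 112. Two-look O'Brien-Fleming boundaries inflate N by 1.008 to 225 in total. The stated 226 is therefore correct for the unadjusted t-test.

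**2. Ideal case, perfect balance.** The t-test reports SE = 4 × √(2/113) = 0.532. The true SE is 0.532 × √(1 − R²). Hence:
- type I error of the t-test = 2Φ(−1.96/√(1 − R²)) = 4.4, 3.4 and 2.4% at R² = 5, 15 and 25%;
- power at R² = 15%, with 1.5/0.532 = 2.819: t-test Φ((2.819 − 1.96)/√0.85) = 82.4%; adjusted model Φ(2.819/√0.85 − 1.96) = 86.4%.

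**3. Simulation with realistic strata.** There were 8,000 trials per row, and the methods were compared on the same data. The Monte Carlo SE is about 0.24 points for type I error and 0.45 for power. Assumptions: permuted blocks of 4 in 32 strata; site shares from 28% down to 4%, with the two smallest pooled; age mean 65, SD 14; lung disease 25%, of whom 30% GOLD C/D; R² split equally over age above 70, lung disease and site. The strata model is linear in treatment, continuous age, lung disease yes/no and site.

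| R² | Type I, t-test | Type I, strata model | Power, t-test | Power, strata model | t-test interval wider by |
|---|---|---|---|---|---|
| 0 | 5.1% | 5.2% | 80.7% | 80.3% | 0% |
| 5% | 4.3% | 4.7% | 79.8% | 80.8% | 2% (SE 0.532/0.522) |
| 15% | 3.5% | 4.6% | 81.9% | 85.4% | 7% (0.532/0.499) |
| 25% | 2.9% | 5.1% | 83.0% | 88.2% | 12% (0.532/0.474) |

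The t-test thus forgoes about 0, 1, 3.5 and 5 points of power.

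**4. Varying the assumptions.**
- R² = 15% from one factor only: age 80.5 vs 85.7% (5.2 points), lung disease 82.3 vs 86.0% (3.7), site 81.8 vs 85.4% (3.6).
- Blocks of 8, R² = 15%: 81.2 vs 84.3% (3.1 points).
- Bounded integer outcome 0 to 14, observed R² about 7, 17 and 28%: type I error of the t-test 4.2, 3.5 and 2.7%; power 80.6 vs 82.1, 82.3 vs 86.2 and 84.7 vs 90.4%.
- Separate simulation with equal sites and 30% lung disease: at R² = 10, 20 and 30%, power 79.9 vs 82.7, 82.4 vs 88.4 and 83.8 vs 92.1%.
- Interim look, n = 113, R² = 15%: SE 0.752 vs 0.711, so the t-test interval is 6% wider.

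**5. Against the SAP's own adjusted model.** Take strata R² = 15% and let sex, heart failure and smoking explain a further 0, 5 or 10%. Power of the SAP model vs the strata model is then 82.0 vs 85.4, 84.3 vs 85.0 and 86.1 vs 84.9%. The sign changes, so no fixed loss against that model can be claimed.

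**The case against.** An unadjusted primary test with a prespecified adjusted analysis beside it is a valid choice, and any error here is conservative. The documents give no R²; at 5% the gain is about 1 point and at 0 there is none. The estimate itself already benefits from the balanced allocation: at R² = 20% its simulated SD was 0.48 unadjusted and 0.47 adjusted. What is lost is correct reporting of that precision.

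The SAP also recovers part of the loss. If the whole 15% comes from a linear age effect, its adjusted model reaches 85.2% against 85.7% for the strata model, although as a supplementary result. Where sex, heart failure and smoking matter more, a model that adds them to the strata is stronger: 88.3% against 84.9% in the row where they explain 10% on top of strata at 15%. For the interim look no test is named, so applying the point there assumes that it would follow the main analysis.

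All of this stands and limits the weight of the point. It does not remove it: the main analysis would still report an interval that disregards the design, and no analysis in the plan uses site or lung disease as stratified as a covariate.

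**Conclusion.** The concern holds, as a matter of efficiency and correct standard errors and not of validity. The treatment estimate is unbiased, false positives are not inflated, and 226 patients give the planned 80% power. If the stratification factors explain 5 to 25% of DAOH14 variance, the t-test forgoes about 1 to 5 points of power and its interval is 2 to 12% wider than that of the strata model. If they explain nothing, nothing is lost. These sizes rest on assumed R², site shares, patient mix and block size; the direction was the same in every variation with prognostic strata. The change should be made because it is nearly free, but the trial does not fail without it.

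**What to change.** The SAP (Introduction) sets its own window: it is written "while enrolment of patients and collection of data is still on-going and before the database is accessed for trial results". Within that window, and before the analysts compare arm A with arm B, issue a dated SAP version that:

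- makes the primary analysis a linear model of DAOH14 on treatment, continuous age, chronic lung disease as stratified (yes/no) and site, reporting the adjusted mean difference with its 95% CI;
- states the rule for pooling small sites, based on numbers randomised and without reference to arm or outcome;
- uses the same model for the 21-day fallback, the 30-day outcome and the interim analysis of DAOH14;
- keeps sex, heart failure and smoking in the supplementary model, and adds site and the lung-disease stratum there;
- keeps the t-test and the Mann-Whitney test as sensitivity analyses, and keeps N = 226.

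Baseline oxygen flow, already in the SAP's baseline list, could be prespecified as one more covariate. With strata at 15%, adding it takes power from 84.9 to 86.7% if it explains 5%, and from 85.4 to 85.3% if it explains nothing.

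Cost: no new data, since age, site and lung disease are needed to randomise. The covariates use 8 or 9 of 224 degrees of freedom (age, lung disease, and 6 or 7 site terms with or without pooling). If the factors explain nothing, power is 80.3% instead of 80.7%. Because the SAP says that it agrees with the approved protocol, Protocol 3.3.6 needs a note that the t-test there is the sample-size basis. The SAP was to be published, so the revised version should be published too. A pooling rule left open would become a choice made after seeing the data.

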## **DATA ANALYSIS**

### **Descriptive analyses – Baseline characteristics at study enrollment (defined as day 1).**

The following baseline characteristics of the study population will be summarized separately within each randomized group:

- Age, median (IQR), y
- Male sex, n (%)
- Ethnicity (Caucasian, African (incl. Afro-American), Asian, Inuit, Unknown/other)
- Body mass index ( $\text{kg}/\text{m}^2$ , median, IQR)
- Current smoker, n (%)
- Ex-smoker, n (%)
- Nonsmoker, n (%)
- Pack-years history (median, IQR, y)
- Use of oxygen therapy, n (%)
- Use of CPAP, n (%)
- Use of noninvasive mechanical ventilation, n (%)
- Infiltrate on Chest X-ray, n (%)
- Oxygen consumption: L/min (median, IQR)
- Oxygen consumption:  $\text{FiO}_2$  (median, IQR)

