### **Subgroup analyses (all according to baseline values)**

Scheduled to perform following stratified analyses for the primary outcome:

- stratified analyzes in the presence of chronic lung disease or not
- stratified analyzes for QTc across the median
- stratified analyzes for < 2L nasal oxygen or ≥ 2L nasal oxygen
- stratified analyzes CRP < 50 mg/L and CRP ≥ 50 mg/L
- stratified analyzes D-dimer > 0.8 mg/L or D-dimer ≥ 0.8 mg/L

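### The adjusted models for days alive and out of hospital and for mortality include no measure of acute COVID-19 severity at entry, although baseline oxygen flow and CRP are already in the plan

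*SAP*

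**What the plan says.** SAP, Primary objective and outcome, makes an unadjusted t-test on DAOH14 the main analysis and adds a general linear model adjusted for "Age (per year increase), sex (M/F), COPD GOLD C/D (Yes vs. No), Heart failure NYHA III-IV (Yes vs. no), Active smoker (Yes vs. No"). Under Secondary objective and outcomes, mortality at 30 days (item 4), 90 days (item 7) and 365 days (item 8) is also examined "as an adjusted analysis using Cox proportional hazards models" with the same five variables. Item 6, DAOH at 30 days, is to be analysed as the primary outcome is, so it takes the list too.

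Severity at entry appears elsewhere in the plan:

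- The SAP baseline table includes "Oxygen consumption: L/min (median, IQR"), as well as FiO2 and use of oxygen. CRP is listed under the biochemistry findings.
- The SAP subgroup section, which uses baseline values, splits the primary outcome at 2 L of nasal oxygen and by CRP: "stratified analyzes CRP < 50 mg/L and CRP ≥ 50 mg/L".
- Protocol 3.3 excludes patients needing more than 5 L/min, so entrants range from no oxygen up to that limit.
- Protocol 3.3.2 stratifies randomisation by age, site and chronic lung disease. No stratum reflects acute severity.

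**The concern.** The endpoint is driven by when a patient leaves hospital alive, and oxygen need at entry is a natural predictor of that. A covariate-adjusted analysis has two uses in a randomised trial: it removes explained variation from the error term, and it corrects for chance differences between arms on prognostic variables. A list made up only of demographic, chronic-disease and smoking variables can do little of either for acute severity.

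Readers will look for a severity imbalance in the baseline table. If they find one, the prespecified adjusted estimate cannot say how much it matters. The SAP also rules out further analysis after unblinding except at the request of reviewers or editors, so a severity adjustment made then would be post hoc.

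**Working it through.** **Inputs.** From Protocol 3.3.6: "Type 1 error rate = 5%. Power = 80%. Two-sided statistics"; difference "Estimated time for improvement/deterioration: 1.5 days"; standard deviation "in patients with lung disease and COVID-19: 4 days (up to 10 days hospitalization"); and "This requires 226 patients randomised 1:1 with 113 in each group". The share of DAOH14 variance explained by severity (R²) and its correlation r with DAOH14 are not in the documents. I assume R² of 0.05-0.25 and r of 0.3-0.5.

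**1. Reproduce the plan's figure.** The standard error of the difference is 4 × √(2/113) = 0.532 days, and the noncentrality is 1.5/0.532 = 2.82. The noncentral t calculation gives 80.1% power, and 113 is the smallest arm size that reaches 80%. The planned 226 is confirmed for the unadjusted test.

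**2. Effect of adding severity.** The residual SD is 4 × √(1 − R²). The 95% interval half-width is 1.97 × residual SD × √(2/113). The last column is 1/(1 − R²) − 1, the proportional increase in patients that would give the same precision.

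| Added R² | Residual SD (days) | 95% CI half-width (days) | Power for 1.5 days | Equivalent extra patients |
|---|---|---|---|---|
| 0 | 4.00 | 1.05 | 80.1% | – |
| 0.05 | 3.90 | 1.02 | 82.1% | 5% |
| 0.10 | 3.79 | 0.99 | 84.1% | 11% |
| 0.20 | 3.58 | 0.94 | 88.1% | 25% |
| 0.25 | 3.46 | 0.91 | 90.0% | 33% |

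The first row is the unadjusted test. It stands in for the present five-covariate model only if those covariates explain nothing. To the extent that they do explain variance, the starting power of the adjusted model is higher than 80.1%.

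**3. Chance imbalance.** The standardised arm difference in a baseline covariate has standard error √(2/113) = 0.133 SD.

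- Exceeded in 1 trial in 20: 1.96 × 0.133 = 0.26 SD. This shifts a difference not adjusted for severity by 0.26 × r × 4 = 0.31 days (r = 0.3) to 0.52 days (r = 0.5), or 21-35% of 1.5 days.
- Median case: 0.674 × 0.133 = 0.09 SD. The shift is 0.11-0.18 days, or 7-12% of 1.5 days.

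**4. Room in the Cox models.** Treatment plus five covariates is six terms; adding oxygen flow makes seven. At the 25% mortality quoted in the Protocol background, 226 × 0.25 ≈ 56 deaths, about 8 per term. At an assumed 5-10% there are 11-23 deaths, about 1.6-3.3 per term. Even the present list could be stretched, which argues for one extra term at most.

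**The case against.** The strongest reply is that the main conclusion does not depend on this. The SAP's main analysis is the unadjusted t-test, and the sample size is built on it. The adjusted model carries no power claim. Chance imbalance is already covered by the t-test's error rate and interval: even the 1-in-20 shift of 0.52 days is below one standard error (0.53 days). All of this stands. A reader might infer from the table that the trial is underpowered, or that the fix buys the trial up to a third more patients. The documents do not support that, because the gain belongs to the supportive analysis only.

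A reader might also infer that every adjusted model in the SAP ignores severity. That is wrong. The analyses of change in PaO2 and PaCO2 (items 11-12) are ANCOVAs on the baseline value, and baseline PaO2 is itself an acute respiratory measure.

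It can further be said that use as a subgroup factor does not prove prognostic value, since QTc is on the same subgroup list. The 5 L/min exclusion narrows the severity range and may shrink the gain. Oxygen flow in home-oxygen users partly reflects chronic disease. Daily blood samples are described as usual care with results taken from the record, so CRP may be missing in some patients. Nor do the documents show that GOLD C/D or NYHA III-IV are rare here. These points limit confidence in the size of the gain, but not in the omission.

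Finally, the planned subgroup splits and baseline table describe severity. They do not produce a severity-adjusted overall estimate.

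**Conclusion.** The concern holds for the adjusted DAOH models (14 and 30 days) and the adjusted mortality models (30, 90 and 365 days). They omit acute severity although suitable baseline variables are at hand and randomisation does not balance on them. It is a weakness in supportive analyses and cheap to repair. It is not an error in the main test, the sample size or the type I error.

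For DAOH14, the adjusted half-width would fall from about 1.05 days to 1.02-0.91, and power would rise from about 80% to 82-90%. That rests on an assumed added R² of 0.05-0.25 and on ignoring what the existing covariates explain. In the Cox models the benefit would be in power and imbalance protection, not in a smaller standard error of the log hazard ratio. I am confident of the omission and much less so of the size.

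**What to change.** In SAP, Primary objective and outcome, add two continuous covariates to the general linear model: baseline oxygen flow in L/min (0 if none) and log baseline CRP. Item 6 (DAOH at 30 days) then follows. State a rule for missing baseline values, for example single imputation from baseline data without regard to arm. In the Cox models (items 4, 7 and 8) add baseline oxygen flow only, because deaths may be few.

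Fix the list before the database is accessed for any comparison of arm A with arm B. Breaking of the code is too late a deadline: the SAP section on blinding of the statistician has all analyses done by masked arm before that point, so covariates could be chosen after comparisons had been seen. The SAP introduction already sets the right standard, that the plan is laid down before the database is accessed for results.

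The cost is a wording change, two extra terms in the linear models, one in each Cox model with fewer events per term, and the missing-value rule. It needs no new data or patients, and the main analysis stays as it is.
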